## 1.0 Objectives / Specific Aims

Our central premise is that survivors must engage in more in-home paretic arm use and less non-paretic arm use because real world use drives neural plasticity more than the limited therapy visits available. We argue that survivors do not use the paretic arm outside of the clinic to maximize beneficial plasticity because post-discharge support from the rehabilitation team is limited, thus survivors do not fully understand why or how to use the paretic arm at home. Although current in/outpatient rehabilitation provides basic education about stroke and managing impairments, current rehabilitation practice does little to empower stroke survivors with knowledge or skills; specifically, knowledge of the neurobiological processes causing the impairment and the requisite skills to manage their own long-term recovery. Our unique interprofessional research team, comprised of experienced stroke rehabilitation providers and a nurse scientist, are award-winning educators and passionately believe that survivors can improve outcomes if supported with knowledge and skills.

Hence, we created a first of its kind multimodal therapy + e-learning program called **Training to Empower Activity-dependent-plasticity-based Arm-use-habits in the Community and at Home** (TEAAC). Here we test its implementation:

### **AIM: Implement the TEAAC program**

*Rationale:* Online training to improve post-discharge self-management skills in community dwelling stroke survivors is a new concept, therefore there is a need to test the feasibility of this approach. *Method:* Twelve (n=12) survivors  $\geq 3$  months post stroke with moderate arm motor impairment, will be enrolled in TEAAC. TEAAC is a cutting-edge therapy + e-learning program designed to gradually transition the stroke survivor away from therapist-management to self-management of long term stroke recovery. TEAAC will have 3 essential components; a behavioral contract signed before the program begins to assure that its focus is explicit in survivors' minds; direct therapist contact for 3 months (3 months in-clinic therapy with online guidance); and online course activities guided by rehabilitation professionals to engage learning and peer mentorship.

### **SA1: Determine the feasibility of implementing the TEAAC program:**

The primary endpoint will be a determination of the feasibility of the e-learning + therapy program. Primary outcome will be feasibility defined as (1) subjects' level of engagement in the program, (2) acceptability, (3) technological literacy, and (4) practicality. Data will be analyzed qualitatively.

### **SA2: Determine the initial efficacy of TEAAC:**

Early indication of efficacy will be determined by TEAAC-related changes in measures of (1) self-confidence and social support, (2) self-management skills, and (3) paretic arm impairment and at-home paretic arm use. Changes scores will be calculated to detect a treatment effect measured from baseline (pre-TEAAC) to post TEAAC (3 months), and at 5-months to assess retention.

Impact: This project addresses a critical gap in the field because it innovatively addresses survivors' skills needed to be the self-managers of their own recovery for the long term. TEAAC has an online platform which means that it could be immediately incorporated into clinical practice, modules could be added to meet other needs such as ongoing wellness education, or it could easily be redesigned to meet similar needs in other patient populations.

## 2.0 Background

### A. SIGNIFICANCE

**A.1. Arm paresis from stroke is a long-term impairment that reduces quality of life:** Most stroke survivors, >75%, exhibit upper extremity (UE) hemiparesis, and only 15% recover fully. The majority of daily activities require 2 hands, thus paresis of one hand reduces independence and quality of life.

**A.2. Paretic arm movement can improve during in-clinic therapy, but survivors fail to use the paretic arm outside of the clinic:** Intensive task-practice therapies enable survivors to recover UE skill. But, as shown in **Figure 1** patients demonstrate persistent hyper-reliance on the non-paretic arm for daily activities.

**A.3. Non-paretic arm use is a behavioral compensatory strategy:** The natural response to impairment of one arm is to compensate by using the other arm for critical life activities. Survivors learn compensatory strategies from rehabilitation therapists and a variety of self-help resources.

**A.4. Over reliance on the non-paretic arm is a behavioral manifestation of an underlying activity-dependent maladaptive plasticity that harms paretic arm recovery:**

Repeated behaviors are supported through increasingly more efficient neural networks. Rodent stroke models link non-paretic limb use to increased neural excitability in the non-lesioned hemisphere through a growth response in the basilar dendrites of pyramidal neurons which triggers new inter-cortical trans-callosal connections resulting in synaptic reorganization in areas that should be associated with paretic arm use. In other words, non-paretic limb use elicits activity-dependent plasticity processes that hijack neural reorganization of motor networks that otherwise could support paretic limb recovery Human TMS studies show that an imbalance between the hemispheres and continued maladaptive processes are strengthened by ongoing use of the non-paretic arm. By continuing to exclusively use the non-paretic arm survivors are impeding their own paretic arm recovery (Figure 2).

**A.5. With paretic arm recovery as the goal, survivors must extensively use the paretic arm to reverse maladaptive plasticity and drive beneficial plasticity:** Therapy alone does not elicit a high enough movement dose for beneficial plasticity because the duration of therapy programs and sessions are limited. To effectively actualize restorative plasticity within the constraints of our current healthcare system, more paretic arm use must happen in the home because therapy alone is not/cannot be enough. Our hypothesis is that patient self-directed in-home paretic arm use drives neural plasticity more than the limited therapy visits available (Figure 3). However, there are very few effective in-home programs except the “transfer package” element of a Constraint Induced Therapy (CIT) program. The transfer

[figure not shown]

Figure 2: Theoretical model upon which this study is based: (1) Lesion affecting motor networks, (2) reduces motor skill of the paretic arm and (3) lessens inhibitory input to the non-lesioned hemisphere. (4) Hyper neural activity in the non-lesioned hemisphere (5) grows inter-cortical connections into motor areas within the lesioned hemisphere and (6) supports use of the non-paretic arm. This state promotes over reliance on the non-paretic arm, increased excitability within the non-lesioned hemisphere, ongoing maladaptive plasticity in motor networks of the lesioned cortex and ongoing paretic arm disuse.

[figure not shown]

### 3.0 Intervention to be studied (if applicable)

The **3-month** intervention studied is called **Training to Empower Activity-dependent-plasticity-based Arm-use-habits in the Community and at Home (TEAAC)**. TEAAC has two components: An Online Educational Course and an In-Clinic Rehabilitation Therapy Program.

The TEAAC design and testing timepoints are indicated in the **figure to the left**. Subjects will be tested (see below) at enrollment (Baseline, evaluation timepoint 1, E1)), at the midpoint of the therapy + online program (1.5 months, E2), immediately following the in-clinic therapy + online program (3 months, E3), and 2 months after the program for follow up (5 months, E4).

**TEAAC e-learning:** 3-months of online educational modules include neuroscience education (based on an effective pain educational model) to improve patient self-efficacy, and strategy-training to improve patients' problem-solving abilities for at-home arm use. The course is live on the MUSC MoodleCE platform.

**TEAAC in-clinic therapy:** 24 in-clinic sessions; 3 times/week for 4 weeks (month 1), 2 times/week for 4 weeks (month 2) and 1 time/week for 4 weeks (month 3) with 200 movement repetitions per session. In our RCTs, this therapy dose required ~1.0-1.5 hours/session. A critical element of TEAAC is the focus on linking in-clinic therapy to out-of-clinic real world paretic arm use via MoodleCE Learning Activities.

	month 1	month 2	month 3	month 4	month 5	month 6	month 7	month 8	month 9	month 10	month 11	month 12
N=12	TEAAC Group 1 (n=4)		TEAAC Group 2 (n=4)			TEAAC Group 3 (n=4)		Group1 f/u tests		Group2 f/u tests		Group3 f/u tests

**Enrollment:** Subjects will begin TEAAC in groups of 4 (ideally. However, as per enrollment logistics, the groups may range from 3-5 subjects). The purpose of group enrollment is to afford opportunity for peer-to-peer interactions within the online learning environment. Peer interactions are strongly beneficial for behavioral change and learning. As shown in **the above timeline**, each group of subjects enrolled will form their own "section" of the online Moodle course. New subjects, in groups of 4, will be enrolled every 2 months forming a separate course section. The purpose of forming new course sections is to assure that the course does not have to pause to allow new enrollees to "catch up." Also, overlapping sections allows peer mentoring by having participants who are at a certain stage of health behavioral change mentor other participants who are at another stage of change. Mentor/mentee activities have been built into the course activities.

**Orientation to the Moodle Learning Platform and the Behavioral Contract:** At the baseline evaluation session (E1), subjects will be oriented to the TEAAC program and its expectations

via an in-person orientation session. They will be shown how to access the Moodle Online Course through the MUSC secure network using either a computer, tablet or phone. Although we intend to have participants use their own preferred device and wifi connection, the budget includes monies for 10 tablets to afford opportunity for subjects without technology to participate. Security: The MUSC MoodleCE platform is behind the MUSC firewall and will allow password protected access only to the research team and participants enrolled in TEAAC. The investigative team has extensive experience with the Moodle platform. Once oriented to the TEAAC program subjects will sign a behavioral contract (akin to the course syllabus) that clearly outlines the program goals, scientific premise and expected behaviors. A behavioral contract is considered a critical element of a “transfer package” method to enhance real-world use of the paretic arm.

Theory guiding TEAAC e-learning design and implementation: Every aspect of the course has been thoughtfully designed for consistency with current theories of health behavior change (Transtheoretical Model) and methods of instructional design (Constructivism operationalized as the revised Blooms Taxonomy). To our knowledge we are the first to fit theories from the typically disparate fields of health behavior and education into a framework guiding a stroke

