- Emotional Support will be assessed using the NIH PROMIS Emotional Support assessment. This 8-item assessment records patient's self-reported view of the frequency (never, rarely, sometimes, usually, always) with which he/she has emotional support from others in areas such as listening, someone to confide it, someone who understands one's problems etc.
- Arm movement impairment will be measured with the Fug-Meyer Assessment of the Upper Extremity, a 30-item assessment that indicates how well a stroke survivor is able to move his/her paretic arm into/out of various postures. Each assessment item is scored on a 3 point ordinal scale (0=unable, 1=partial ability, 2=near normal ability), and the item ratings are totaled and reported out of 60 points so that higher scores indicate less impairment (i.e., more ability).
- Arm motor function will be measured with the Wolf Motor Function Test (WMFT), a 15-item assessment indicating the speed at which a stroke survivor can move the paretic arm to complete functional tasks such as stacking checkers or picking up a soda can. Each assessment item is timed, and the average time per item is reported in seconds so that lower scores indicate greater functional ability.
- Paretic arm use in the home will be measured with wrist worn accelerometers. Subjects will be issued 2 accelerometers which are worn on each wrist for 48 hrs. They are the size of an Apple Watch. Subjects will either bring the devices back to the research center at their next visit or mail them back in mailers that we will provide (we pay postage). 3-D acceleration data will be downloaded and used to calculate variables that indicate the acceleration of the paretic arm relative to the non-paretic arm. A neurologically healthy

individual will have values close to 1 to indicate bimanual arm use, smaller numbers indicate less use of the paretic arm, i.e., over-reliance on the non-paretic arm.

- Difficulty using the paretic arm during daily activities will be assessed with the Stroke Impact Scale – Hand subtest. This is a 5-item assessment in which the patient reports the amount of difficulty using the paretic hand along an ordinal scale (0=no difficulty, 5=great difficulty).

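### If accelerometers are issued at the baseline visit, most or all of the 48-hour baseline wear follows orientation and the behavioral contract, so baseline home arm use is not securely pre-TEAAC

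*Combined protocol and SAP*

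**What the plan says.** **Orientation and contract.** Section 3.0 (Orientation to the Moodle Learning Platform and the Behavioral Contract) states: "At the baseline evaluation session (E1), subjects will be oriented to the TEAAC program and its expectations". It then adds: "Once oriented to the TEAAC program subjects will sign a behavioral contract (akin to the course syllabus) that clearly outlines the program goals". The contract is described as a document "that clearly outlines the program goals, scientific premise and expected behaviors", and as a critical element of a "method to enhance real-world use of the paretic arm".

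**Baseline testing.** Section 3.0 also says: "Subjects will be tested (see below) at enrollment", and labels that timepoint E1.

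**Accelerometry.** The schedule of events in Section 10.0 lists wrist accelerometry at E1, E2, E3 and E4, as the measure of paretic arm use in the home. The data collection text says: "Subjects will be issued 2 accelerometers which are worn on each wrist for 48 hrs". Devices come back at the next visit or in a prepaid mailer.

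**What counts as TEAAC.** The Aim in Section 1.0 says: "TEAAC will have 3 essential components; a behavioral contract signed before the program begins to assure that its focus is explicit in" survivors' minds. Section 3.0 says: "TEAAC has two components: An Online Educational Course and an In-Clinic Rehabilitation Therapy Program".

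**Use of the baseline.** SA2 in Section 1.0 plans change scores from a baseline it labels pre-TEAAC to 3 months, and again at 5 months for retention. Section 12.0 describes efficacy by plotting the repeated measures.

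**The concern.** Most baseline tests can be finished within a visit, before the subject is oriented. A 48-hour wear period that starts at the visit cannot. If orientation and signing take place at the same session, the subject goes home wearing the devices after being told the rationale for using the paretic arm and agreeing to the behaviors expected. That agreement is aimed at the construct the devices record.

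The design is a single longitudinal cohort (Section 10.0), so no control group can absorb a shifted baseline. Each subject's own E1 value is the only reference for change in home arm use. If the contract raises arm use at once, part of the program's effect is counted as baseline and the later change looks smaller than it was.

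The two lists of components add to the difficulty. With three components the contract belongs to TEAAC; with two it does not. The label pre-TEAAC therefore has no single meaning.

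**Working it through.** The plan gives no figure on this point to reproduce. The check has three parts: the order of events, the exposed share of the wear, and how a shift would carry into the change scores.

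**1. Order of events**

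| Event | Timing in the plan | Where |
|---|---|---|
| Baseline tests | E1, at enrollment | Section 3.0 |
| Orientation | At the E1 session | Section 3.0 |
| Contract signed | Once oriented; before the program begins | Sections 3.0 and 1.0 |
| Baseline accelerometry | E1; issued, worn 48 h, returned at the next visit or by mail | Section 10.0 |
| First module or therapy session | No interval from E1 stated | – |

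Return at the next visit or by mail means that wear follows the visit of issue. The text describes no issue before E1 and no delay of signing until wear ends. Eligibility depends partly on the baseline Fugl-Meyer score and on judgement at baseline testing (Section 5.0), which makes earlier issue less likely. The order within E1 is not stated, and the figure of testing timepoints was not available for this review, so the sequence is an inference.

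**2. Share of the wear that follows the contract**

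Input from the plan: 48 hours of wear. Assumed input: h, the hours from start of wear to signature. The plan does not give h; small values correspond to signing in the same session.

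Share = (48 − h)/48

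| h (assumed) | Calculation | Share after the contract |
|---|---|---|
| 0 | 48/48 | 100% |
| 1 | 47/48 | 97.9% |
| 2 | 46/48 | 95.8% |
| 4 | 44/48 | 91.7% |
| 8 | 40/48 | 83.3% |

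If the wear is completed before signing, the share is 0%. For any one-day session that starts with device issue, the share is most or all of the wear.

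**3. Effect on the change scores**

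Let d be any rise in the recorded E1 value caused by orientation and the contract.

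- Observed E3 − E1 = true (E3 − E1) − d
- Observed E4 − E1 = true (E4 − E1) − d
- Observed E4 − E3 is unchanged, because E1 does not enter it

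A positive d therefore understates both changes from baseline by the same amount. One of the four plotted accelerometry points (E1) is exposed. The documents give no value for d, so no effect size is computed.

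**The case against.** **The sequence is inferred.** Nothing says outright that devices are handed out at E1, or that the contract is signed that day. Section 9.0 describes a scheduled consent appointment and does not say it is the E1 visit, so issue at consent is not excluded. Signing after the wear would satisfy both Section 3.0 and Section 1.0. This stands as a limit: exposure could be 0%. But neither alternative is written as the plan's procedure, and the natural reading leads to exposure.

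**On the two-component definition, the wear may still be pre-program.** This stands in part. Section 1.0 also calls the contract essential, and no interval between E1 and the first module or session is given, so even the narrower reading is not secured.

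**The effect may be negligible.** The protocol's own model allows for this. Table 2 matches the first course unit to precontemplation, and the theory text puts overt home use in the later action stage. No passage says that signing alone changes arm use within 48 hours. This stands, and it is why no size is claimed.

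**The consequence is small.** Accelerometry is one secondary measure among several in a 12-subject feasibility study, described by plots. A contract-driven rise at baseline would understate benefit; it would not create a false one. This stands and sets the priority.

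**The remedy has a cost and is partial.** Moving orientation out of E1 changes a sentence in Section 3.0 and may add a visit for people who already attend 24 sessions. Consent follows a review of the protocol (Section 9.0), so subjects already know about the study. Reordering removes only what orientation and the contract add to consent.

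**Conclusion.** The concern holds in its conditional form. If devices are issued at E1 and the contract is signed at that session, 92% to 100% of the baseline wear follows signing, for assumed delays of 0 to 4 hours. The baseline for home arm use is then not securely pre-TEAAC.

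This rests on three things: issue at E1 (the natural reading, not stated), signing in the same session (likewise), and treating the contract as part of TEAAC, as Section 1.0 does. Whether arm use actually rises in those 48 hours is unknown, and the bias may be zero. If there is a rise, the changes from E1 to E3 and from E1 to E4 are understated, while the change from E3 to E4 is not affected.

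The order of the other baseline measures relative to orientation is not stated either, but those can be completed first within the visit. The primary endpoint and N=12 are untouched. This is a point to consider, held with medium confidence.

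**What to change.** 1. State the order of procedures at E1, with all in-person baseline tests before orientation.
2. Issue the devices after E1 testing, and hold orientation and contract signing until the 48-hour wear is complete, for example at device return or at the first program visit. This still meets the Section 1.0 requirement that signing precede the program. The Section 3.0 sentence placing orientation at E1 would need revision.
3. If that is not feasible, record the dates and times of signing and of wear for each subject, and report that baseline wear followed the contract.
4. Reconcile Sections 1.0 and 3.0 on whether the contract is a component of TEAAC, so that pre-TEAAC has one meaning.

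The cost is low: a gap of at least 48 hours between device issue and signing, and possibly one added visit or mailing (prepaid return mailers are already planned). Recording the dates instead costs almost nothing, but it only discloses the problem and does not remove it.

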**Table 2: TEAAC Course Organization**

[figure not shown]
Stage of Behavioral Change Transtheoretical Model	Instructional Design Processes Blooms Taxonomy	TEAAC Online Course Unit (dose)	Learning Objectives  At the conclusion of this unit of instruction the stroke survivor will....	Examples of Moodle Course Features and Learning Activities:
Precontemplation and initial contemplation: unaware of the need to self-manage arm recovery	Remembering: facts, definitions, lists	A (1 activity per week for 1 month)	... demonstrate the ability to log into and interact within the Moodle course  ... list several ways that a stroke changes the brain and body  ... define “recovery”	Assignment: with therapist and course instructor assistance learn to use the Moodle course  WebX Classroom: Stroke 101 WebX Mentee Meeting: Led by survivors Moodle Wiki: begin collection of web pages, definitions and resources that is added to throughout the course
Contemplation: become aware of need	Understanding: interpreting, summarizing	B (2 activities per week for 1 month)	... discuss the reasons why having a stroke causes arm paresis  ... define activity-dependent plasticity and give examples  ... report successful paretic arm use to the group.	WebX Classroom: Learned Arm Disuse Assignment: review baseline assessment results with therapist Assignment: with therapist assist, use paretic arm for new task Discussion Board: group discussion on motivations for using and not using the paretic arm Quiz - Automatic Feedback: survivors' reflect on own learning
Preparation: initial skill acquisition	Applying: implementing, executing	C (3 activities per week for 1 month)	... discuss the link between using the “good” arm and recovery of the “bad” arm  ... implement guided training strategy with progressively less assistance	WebX Classroom: Use It or Lose It: principles from neuroscience WebX Mentee Meeting: Survivors enrolled in another section will lead the meeting Moodle Workshop: survivors post video of self using paretic arm and receive peer assessment.
Action: overtly engaged in skill acquisition	Analyzing: organizing, classifying, differentiating	D (3 activities per week for 1 month)	... analyze at-home activities in order to use the paretic arm independently  ... discuss reasons why using the paretic arm is easier/harder at-home vs. in therapy	WebX Classroom: How often do stroke survivors use the paretic arm compared to people who have not had a stroke? Readings: arm use and recovery Discussion Board: report at-home paretic arm use to the group and discuss
	Evaluating: checking, recommending	E (3 activities per week for 1 month)	.... recommend “tips and tricks” for using the paretic arm at-home to others in the course based on your own successes	WebX Classroom: Non paretic arm use vs. Paretic arm use WebX Mentor Meeting with survivors enrolled in other sections: lead mentoring discussion. Video Forum: asynchronous video chat about ongoing successes and struggles for at home paretic arm use.
Maintenance: sustained self-management skills	Creating: generating, planning	F (1 activity per week for 1 month)	... design new challenges for using the paretic arm  ... generate plans for increased at-home arm use	WebX Classroom: Assuring long term success Moodle Chat: real-time synchronous discussions about goals and plans for long term success. Quiz - Automatic Feedback: survivors' reflect on own learning

rehabilitation program. Stroke survivors do not use their paretic arm during non-clinic times, a learned behavior with a maladaptive plasticity substrate. Increased use of the arm to elicit a beneficial activity-dependent plasticity to support further arm recovery requires that the survivor undergo a behavioral change, from paretic arm *dis-use* to paretic arm *use*. New patterns of behavior must be learned, i.e., must be taught. The Transtheoretical Model of Health Behavior

Change defines 5 stages of behavioral change, which applied to stroke survivors are; (1) precontemplation, a stage in which stroke survivors are unaware of the negative neural consequences of ongoing paretic arm disuse, they await the rehabilitation team's intervention to provide a "cure", and thus have no reason to drive their own long term recovery; (2) contemplation: through the interactions with study team and peers, survivors become aware of the need to self-manage paretic arm recovery but may be ambivalent and lack self-confidence; (3) preparation: as the course and in-clinic therapy sessions begin, survivors take small steps toward self-management as they begin to develop skills and intentional behaviors; (4) action: as the course gets underway the survivor overtly engages in paretic arm use both in-clinic and at home as he/she acquires the new skills needed to manage arm use; (5) maintenance: the survivor demonstrates sustained self-management skills, is able to use his/her paretic arm in daily life activities. The educational theory of Constructivism, operationalized in the revised Bloom's Taxonomy, provides an overall framework from which to develop learning activities to progress survivors through the 5 stages of change. Constructivist theorists propose that learning is optimized when the learner seeks to accomplish a clear goal then engages in a problem-solving process to achieve that goal. As the learner iteratively engages in this problem solving process, he/she receives feedback from him/herself, instructors and peers about his/her skill or understanding which empowers the learner to construct his/her own knowledge. The revised Booms Taxonomy operationalizes Constructivism principles with verbs to indicate progressively more complex problem solving learning processes. Bloom's taxonomy guided TEAACCH learning objectives and learning activities.

TEAACCH MoodleCE Course Organization: The table above presents the course organization. There will be 6 instructional units (A-F) incorporated into this 3-month e-learning course. Each unit is tailored to a stage of behavioral change. Columns 1-3 illustrate how course units relate to stages of behavioral change and instructional design processes. Example learning objectives (column 4) and learning activities (column 5) show the link to the corresponding stage of behavioral change. Each unit's learning activities will leverage various features of the Moodle platform to address the unit objectives through engaging learning activities to (a) develop survivors' knowledge of concepts and facts about stroke recovery and (b) enable acquisition of survivors' problem-solving skills for paretic arm use.

TEAACCH In-Clinic Therapy: Subjects will receive 24 in-clinic Targeted Task Practice rehabilitation sessions; 3 times/week for 4 weeks (month 1), 2 times/week for 4 weeks (month 2), 1 time/week for 4 weeks (month 3) with 200 movement repetitions per session which, in our recently completed RCT of this intervention, required ~1.0-1.5 hours/session, consistent with the literature. The content of the therapy sessions will be individualized according to each participants' score on the Fugl-Meyer Assessment of the Upper Extremity Keyform according to the procedures followed in our

previous VA Merit Award, and that we have published. We call this therapy approach Targeted Task Practice. The distinguishing feature of this intervention is that the Fugl-Meyer Assessment of the Upper Extremity (FMA-UE) Keyform is used to individualize the content of therapy sessions to assure that all task-practice will occur at the optimal level of difficulty for each patient. The procedure for using the keyform to individualize treatment sessions is **illustrated above** as a 4 step process which is also detailed in a recent publication. (1) First, the FMA-UE will be administered in a standardized manner and videotaped. The therapist will score the FMA-UE by circling item ratings on the keyform. (2) Second, the therapist will identify the transition zone by following the consistent pattern of ratings at the bottom of the keyform upwards until it deviated to the next lower adjacent rating (e.g., from a rating of 2 to 1, or from a rating of 1 to 0). This deviation will mark the lower boundary of the transition zone which is defined as the first 5 consecutive items for which 3 of these items received the next lowest rating. These 5 items represent the expected next steps in the subject's transition from a current skill level to a greater skill level, therefore they will be the movements to target in the task practice therapy sessions. (3) Third, to assure the functional relevance of the rehabilitation program the 5-transition zone paretic arm motions will be practiced within the context of functional activities so that they will not be disconnected from their functional application. In our previous Merit project, we developed a detailed study-specific Treatment Activity Menu which links each of the 30 FMA-UE voluntary movement items to functional tasks that primarily require the item's arm movement. We will use this manual in the proposed study. The therapist and subject will collaborate to identify 2 functional activities from the Treatment Activity Menu for each of the 5 target movements identified by the keyform transition zone (total of 10 functional activities). An example of this menu is shown in the figure. As shown, the menu links the FMA-UE item "scapular retraction" to the functional tasks "Donning a long-sleeved jacket" and "household cleaning" because the tasks naturally require repetition of the targeted movement. (4) Finally, as shown in the photos, subjects will perform 20 repetitions of each movement target within each functional activity for a total of 200 repetitions/session. The number of repetitions is based on work indicating its feasibility, safety and effectiveness. The process of scoring the keyform, locating the transition zone, identifying targets and choosing functional activities required ~15 minutes in our previous studies. To assure systematic task difficulty progression throughout the in-clinic program, subjects will be reassessed with the FMA-UE keyform weekly to identify new therapy targets and functional activities. The expectation is that as ability increases, the keyform transition zone will shift upwards to identify 5 new, slightly more difficult targets.

Assurance of patient safety during in-clinic sessions: Therapy sessions will be conducted by a licensed occupational therapist. Heart rate and blood pressure will be recorded before, during and after each session and the study therapist will closely monitor the subject for possible pain or fatigue. In previous work we demonstrated that the functional tasks practiced in a session were at a difficulty level that matched or slightly exceeded the subjects' movement ability level, therefore we do not expect that the patient will show movement compensations. To further assure that movement compensations do not emerge and cause pain or injury, aspects of each task such as object weight, speed of performance or surface heights will be manipulated by the therapist.

A critical element of TEAAC is the focus on linking in-clinic therapy to out-of-clinic real world paretic arm use via MoodleCE Learning Activities: In-clinic therapy for TEAAC subjects will incorporate "guided training" methods into the task practice therapy sessions to elicit survivors' self-reflection and self-efficacy. Guided training is an emerging, effective method to train independent problem-solving abilities via self-instruction, self-monitoring, self-evaluation, and self-rewarding. The therapist will teach a "goal-plan-do-check" process, which will then be practiced throughout therapy. Specifically, before the start of each functional task, with the

assistance of the therapist as needed, participants will instruct themselves what to do (set goal) and how to do it with the paretic arm (develop a plan). The subject does the task and then checks whether the plan worked. For example, if the task is to “set the table” the subject would identify the goal (put the plates there, and the cups there) and how to accomplish it (by reaching forward and straightening my affected arm). After doing it, the therapist will prompt the participant to register if they (1) used the paretic arm, (2) used it in the specified manner (targeted motions), (3) could do it better or differently the next time, and (4) give one’s self a pat on the back if it was done well. This process will be repeated iteratively throughout in-clinic sessions and progressively faded over the 3 months in-clinic program. MoodleCE assignments will reinforce guided training. For example, a discussion board activity will ask participants to reflect on one’s skill implementing the guided training strategy, a mentor meeting will center sharing one’s own successes/challenges in implementing this strategy, and a video forum will show examples of this process in action.

